3.1 Inclusion Criteria

Informed Consent

- ___ 1. Documented informed consent of the participant and/or legally authorized representative.
 - Assent, when appropriate, will be obtained per institutional guidelines

Age Criteria, Performance status

- ___ 2. Age: ≥ 18 years
- ___ 3. Patients must have a life expectancy of > 3 months
- ___ 4. ECOG ≤ 2

Nature of Illness and Illness Related Criteria

- ___ 5. Patients must have a diagnosis of cutaneous CD30+LYPD
- ___ 6. Patients must be relapsed or are refractory to at least 1 prior line of therapy
- ___ 7. At least 2 weeks from prior therapy to time of start of treatment. Prior therapy includes steroids (except prednisone or equivalent – up to 10 mg/day is allowed).

Clinical Laboratory and Organ Function Criteria (To be performed within 21 days prior to Day 1 of protocol therapy unless otherwise stated [see Section 10.0])

 ___ 8. ANC $\geq 1000/\text{mm}^3$ NOTE: Growth factor is not permitted within 14 days of ANC assessment unless cytopenia is secondary to disease involvement. 	ANC: 	Date:

 ___ 9. Platelets $\geq 50,000/\text{mm}^3$ NOTE: Platelet transfusions are not permitted within 14 days of platelet assessment unless cytopenia is secondary to disease involvement. 	Plts: 	Date:

 ___ 10. ___ 10. Total bilirubin $\leq 1.5 \times \text{ULN}$ (unless has Gilbert's disease) 	ULN: Bil: 	Date:

 ___ 11. AST $\leq 2.0 \times \text{ULN}$ 	ULN: AST: 	Date:

 ___ 12. ALT $\leq 2.0 \times \text{ULN}$ 	ULN: ALT: 	Date:

 ___ 13. Creatinine clearance of $\geq 30 \text{ mL/min}$ per 24 hour urine test or the Cockcroft-Gault formula or $\text{CrCl (mL/min)} = \frac{(140-\text{age}) \times \text{actual body weight (kg)}}{72 \times \text{serum creatinine (mg/dL)}} \times 0.85 \text{ for females}$ 
Or
 $\text{CrCl (mL/min)} = \frac{(140-\text{age}) \times \text{actual body weight (kg)}}{0.8136 \times \text{serum creatinine (umol/L)}} \times 0.85 \text{ for females}$ 	Serum Cr: Cr Clearance: 	Date:

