
___ 14. Seronegative for HIV Ag/Ab combo, HCV*, active HBV (Surface Antigen Negative) *If positive, Hepatitis C RNA quantitation must be performed.
 
___ 15. Meets other institutional and federal requirements for infectious disease titer requirements Note Infectious disease testing to be performed within 28 days prior to Day 1 of protocol therapy.
 
___ 16. Negative for tuberculosis antigen (e.g. T-Spot test).
 
___ 17. Women of childbearing potential (WOCBP): negative urine or serum pregnancy test If the urine test is positive or cannot be confirmed as negative, a serum pregnancy test will be required
	
HIV: HCV: HBV: Syphilis:
 
Urine: Serum: Date:
	
Date:

Contraception

___ 18. Agreement by females **and** males of childbearing potential* to use an effective method of birth control (hormonal or barrier method of birth control or abstinence) or abstain from heterosexual activity for the course of the study through at least three months after the last dose of protocol therapy. The effects of study treatment on a developing fetus have the potential for teratogenic or abortifacient effects. Should a woman become pregnant or suspect that she is pregnant while participating on the trial, she should inform her treating physician immediately.

* Childbearing potential defined as not being surgically sterilized (men and women) or have not been free from menses for > 2 years (women only).

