10.0 STUDY CALENDAR

Table 10 describes required procedures. All procedures may increase in frequency if clinically indicated or oriented following toxicity. Adjustments to the treatment cycle due to a hold in study agent are detailed in [Section 5.2](#).

Table 10.0 Study Activity Calendar

	Screen -ing ^a	Cycle 1, 2, 3		Cycle 4+ Day 1 ^d	End of Treatment ^e				Active Follow-Up ^j
		Day 1 ^b	Day 14 ^c		Day 0 ^f	Days 1-11 ^g	Day 14 ^h	Day 30 ⁱ	
Informed Consent ^k	X ^s								
Inclusion/Exclusion Criteria ^l	X								
Registration ^m	X ⁿ								
Medical history ⁿ	X								
Physical exam	X	X		X				X	
Vital signs ^o	X	X		X				X	
Adverse events assessment ^p		X	X	X	X	X		X	
Concomitant meds review	X	X		X	X			X	
ECOG status (Appendix A) ^q	X	X		X				X	
Pregnancy test ^q	X								
TB antigen test ^r	X								
Hepatitis A, B, C testing	X ^s								
Skin photographs ^t	X	X		X	X			X	X
mSWAT ^u	X	X		X	X			X	X
Skin biopsy ^v		X ^w		X ^w				X ^w	
CBC with differential ^x	X	X	X	X				X	X
Chemistry panel ^y	X	X	X	X				X	X
Response assessment ^z		X		X	X			X	X
Teriflunomide clinical testing ^{aa}				X			X ^{dd}	X ^{dd}	
Leflunomide administration ^{bb}		Daily							
Cholestyramine ^g						X ^g			

- a. All screening procedures to be performed within 21 days of start of study agent except informed consent, acute hepatitis panel, skeletal survey which may occur within 30 days of start of treatment (footnote u) and except for registration which must occur within 7 days from start of treatment (footnote n).
- b. Day 1 assessments to be performed within 5 days (120 hours) prior to Day 1 drug (except footnote u for C1 only). Day 1 safety assessments must be resulted and reviewed prior to administration of agent for the cycle that is initiating. Screening assessments, if performed within this aforementioned time frame, may serve as C1D1 assessments. Note: items with footnote "aa" are not performed for C1D1; the windows for screening assessments still apply.
- c. Day 14 evaluations have +/- 3 day window.
- d. Day 1 assessments to be performed within 5 days (120 hours) prior to Day 1 drug. Day 1 safety assessments must be resulted and reviewed prior to administration of agent for the cycle that is initiating.
- e. Reasons to end study treatment include disease progression and unacceptable toxicity. See Section 5.8 for all criteria.

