- n. Medical history to include review treatment history for CD30+LYPD medical history pertaining to eligibility, and demographic information.
- o. Vital signs: Weight, heart rate, blood pressure, respiration rate, temp. Height required only at baseline.

- p. Adverse event (AE) reporting begins for events that occur after start of study agent. AE recording and reporting will continue until the completion of the EOT Day 30 visit or until resolution or stabilization of any serious AE occurring before the completion the EOT Day 30 assessments, which every occurs later.
- q. Serum or urine pregnancy test for women of child bearing potential only.
- r. T-Spot or other TB antigen test.
- s. Consent, acute hepatitis panel, to be completed within 30 days prior to registration.
- t. Skin photographs: for subjects with skin lesions, up to five designated index lesions, representative of the subject's extent of disease, will be selected at baseline and measured and photographed using a digital camera. Photos should be taken against a blue backdrop. The photos will be taken on Day 1, prior to the first dose and then Cycle 2 Day 1 (-7 days) then every Cycle. In addition, half-body global photos (waist to feet, waist to top of head and sides) will also be obtained. Photos must be labeled with patient's protocol number and initials.
- u. Modified Severity Weighted Assessment Tool (mSWAT)[30] ([Appendix C](#))
- v. skin biopsies for research will not be taken at baseline if patients have a recent biopsy taken containing needed information.
- w. skin biopsies for research at baseline, at C2D1, C5D1, and EOT (if lesions are present), and at disease progression ([Section 9.2](#)).
- x. CBC with differential: erythrocytes (RBC), hemoglobin, hematocrit, platelets, total WBC plus absolute differential counts (neutrophils, lymphocytes, monocytes, eosinophils, basophils).
- y. Serum chemistry panel: Comprehensive metabolic panel (sodium, potassium, chloride, carbon dioxide, creatinine, urea nitrogen, calcium, glucose, albumin, total bilirubin, alkaline phosphatase, total protein, ALT/SGPT, AST/SGOT) LDH, magnesium, phosphorus, and uric acid.
- z. See [Section 11.2](#) for response assessment criteria.
- aa. Teriflunomide clinical blood assay to be ordered as "leflunomide metabolite" miscellaneous clinical test.

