17.6 Special and Vulnerable Populations

17.6.1 Women and Minorities

The study is open to anyone regardless of gender, race or ethnicity. Efforts will be made to extend the accrual to a representative population. If differences in outcome that correlate to gender, racial, or ethnic identity are noted, accrual may be expanded or additional studies may be performed to investigate those differences more fully.

Pregnant women are excluded because the study drugs have been determined to be embryolethal and teratogenic in animal testing.

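### The only scheduled pregnancy test may be up to 21 days old at the first dose, 16 days older than the Day 1 CBC and chemistry may be

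*Combined protocol and SAP*

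**What the plan says.** Exclusion criterion 10 in Section 3.2 bars pregnant women because of possible teratogenic or abortifacient effects. Section 17.6.1 repeats the reason: "Pregnant women are excluded because the study drugs have been determined to be embryolethal and teratogenic in animal testing".

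The check on that exclusion is item 17 of Section 3.1, a "negative urine or serum pregnancy test" for women of childbearing potential, with a serum test if the urine result is positive or unclear. The item states no timing. It falls under the heading for laboratory criteria, which reads "To be performed within 21 days prior to Day 1 of protocol therapy unless otherwise stated".

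In Table 10 (Section 10.0) the row "Pregnancy test ^q" has one mark, in the Screening column. Footnote q says only "Serum or urine pregnancy test for women of child bearing potential only". Footnote a sets the window: "All screening procedures to be performed within 21 days of start of study agent". The footnote allows 30 days for consent, the hepatitis panel and a skeletal survey, and it sets a separate 7-day limit for registration. The pregnancy test is not among those exceptions.

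CBC with differential and the chemistry panel are marked at Screening and again on Day 1. Footnote b governs the second set: "Day 1 assessments to be performed within 5 days (120 hours) prior to Day 1 drug". It also requires Day 1 safety results to be available and reviewed before that cycle's drug is given. A screening assessment done within the 5 days may count as the Cycle 1 Day 1 assessment.

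**The concern.** Pregnancy status can change between screening and first dose, and a test describes only the day on which it was done. The exclusion is meant to hold when exposure begins, and Section 5.3.1 has exposure begin with three daily loading doses of 100 mg. The plan requires no test close to that moment. A woman who tested negative at the start of the screening window and conceived afterwards would satisfy item 17. The Day 1 review would not reveal the pregnancy, because the pregnancy test is not one of the Day 1 items.

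The protocol recognises this kind of change elsewhere. Exclusion criterion 2 removes eligibility if growth factor or transfusion support is given between screening and the start of treatment. Pregnancy has no comparable check by test. Table 10 schedules no later pregnancy test, so a pregnancy missed at entry would come to light only through symptoms, the participant's own report or unscheduled testing.

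What is at stake is a fetal risk at entry that could be reduced by re-timing a test the plan already includes. No endpoint, sample size or analysis is affected.

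**Working it through.** The documents give no figure to reproduce. The check sets the scheduling rules side by side and takes one difference.

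**Which window applies to the pregnancy test**
- The Section 3.1 laboratory heading gives 21 days before Day 1 unless an item states otherwise.
- Some items do state otherwise. The note at item 15 gives infectious disease testing 28 days. Item 17 has no such note, so 21 days stands.
- Table 10 footnote a gives 21 days for screening procedures, and none of its exceptions is the pregnancy test. Footnote q is silent on timing.
- The two sections agree with each other.

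**Scheduled procedures in Table 10**

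| Procedure | Screening | Cycle 1 Day 1 | Oldest permitted result at first dose |
|---|---|---|---|
| Pregnancy test | yes | no | 21 days |
| CBC with differential | yes | yes | 5 days |
| Chemistry panel | yes | yes | 5 days |
| TB antigen test | yes | no | 21 days |
| Hepatitis panel | yes | no | 30 days (footnote a) |

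Scheduled pregnancy tests: 1, at Screening. Scheduled on Cycle 1 Day 1 or later: 0.

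**Difference in permitted age**

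21 days (pregnancy test) − 5 days (CBC, chemistry) = 16 days.

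**Interaction with registration**
- Section 4.2.3 and footnote m require eligibility to be documented before registration.
- Footnotes a and m allow up to 7 days between registration and treatment.
- If the single test had to fall within the 5-day window, it could not precede a registration made 7 or 6 days before first dose (7 − 5 = 2 such days). For registrations in the last 5 days, one test could serve both purposes.

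Re-timing the test is therefore not purely a change to one table cell.

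**The case against.** The strongest counter-argument is item 18, directly below item 17. Agreement to effective contraception or abstinence is a condition of entry, and a woman who suspects pregnancy must tell her physician at once. Conception between the test and first dose would then usually require contraceptive failure, non-adherence, or a reading under which the agreement starts only with dosing. Exclusion criterion 10 also bars a woman known to be pregnant, whatever the date of her test. Sites may test later within the 21 days, and Table 10 permits more frequent procedures when clinically indicated.

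All of this lowers the risk, and it stands. It does not close the gap. Item 18 is an agreement, not a test. It runs for the course of the study without saying that contraception must begin before dosing. The protocol asks for a test as well as contraception, so it does not treat contraception as sufficient. Later or repeated testing is allowed but not required.

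Two further objections are correct and limit the point. The 5-day rule does not cover every laboratory test, since the TB and hepatitis tests are also screening-only; the comparison is with CBC and chemistry. And a test nearer to Day 1 would still miss a very early pregnancy, so re-timing shortens the unverified interval without removing it.

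A reader might also infer a long fetal exposure from the statement in Section 2.2 that the metabolite may take up to 2 years to become undetectable. That figure is for patients who have no elimination procedure. Section 5.5 gives all participants cholestyramine when treatment ends, followed by metabolite testing, so the figure should not be used to size this concern.

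**Conclusion.** The point holds. Following the plan exactly allows a negative pregnancy test up to 21 days old at first dose, 16 days older than the oldest permitted Day 1 CBC or chemistry, for a drug whose reproductive toxicity is the stated reason for the exclusion. The result rests only on the windows in Section 3.1 and Table 10 and on the absence of any other scheduled test.

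Three stronger readings are not supported.
- **That the documents contradict themselves.** They do not. Section 3.1 and Table 10 agree on 21 days. The weakness is that this timing fits poorly with the purpose of the exclusion and with the pre-dose review.
- **That a longer period of undetectable conception can be stated as a finding.** With an assumed detection lag of 10 to 14 days, the period would be 21 + 10 = 31 to 21 + 14 = 35 days, against 5 + 10 = 15 to 5 + 14 = 19 days under the Day 1 window. The lag is not in the documents. The difference is 16 days whatever lag is assumed (31 − 15 = 35 − 19 = 16).
- **That exposed pregnancies are likely in this trial.** Accrual is at most 14, and the documents do not say how many participants will be women of childbearing potential. Together with item 18, this suggests a low expected number of events, and no frequency can be derived.

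The change is worth making because it is inexpensive and the possible harm is serious, not because the event is expected to be common.

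**What to change.** Reconcile item 17 and the pregnancy row of Table 10 with exclusion criterion 10, Section 17.6.1 and the pre-dose review in footnote b. One way is to list the pregnancy test among the existing Day 1 safety assessments for Cycle 1, so that its result is reviewed before drug is given. Footnote b already lets a screening test done within that window count, so many participants would still need only one test. The sponsor should set the interval and state it identically in item 17, Table 10 and footnote q.

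The registration rules must be aligned in the same amendment. If the 5-day window were adopted, a participant registered 7 or 6 days before treatment would need either later registration or a repeat test. Section 4.2.3 and footnotes a and m should say which applies.

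It would also help to state in item 18 when the contraception commitment begins relative to the screening test.

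**Cost:** short wording changes in item 17, Table 10 and the registration text, and an occasional repeat test. A positive result may be found later in screening, after other screening work has been done. Very early pregnancies may still be missed. Sample size, endpoints, dosing and analysis are unchanged.

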5.5 End of Treatment Evaluations and Leflunomide Detoxification

All participants will be followed until resolution or stabilization of any serious adverse events occurring during treatment and completion of the Day 30 End of Treatment assessments. See [Section 10](#) for a list of all assessments and windows.

Because of the ability of leflunomide to be reabsorbed through the colon, resulting in a very long half-life, all participants will be treated with cholestyramine to prevent re-absorption of leflunomide after the decision to end study treatment has been made.

Participants removed from study treatment will undergo oral administration of cholestyramine 8 grams oral suspension three times daily for 11 days. It will not be a deviation if an administration of cholestyramine is delayed or if the 11 days are not consecutive. Cholestyramine administration may be adjusted per the discretion of the treating investigator. After the treatment with cholestyramine, clinical laboratory testing will be performed to verify plasma levels less than 0.02 mg/L or 0.02 μ g/mL by two separate tests at least 14 days apart. If plasma levels are higher than 0.02 mg/L or 0.02 μ g/mL, additional cholestyramine treatment will be considered. See Section 10 for a tabular view of cholestyramine administration and metabolite testing windows and days of administration.

Note: Cholestyramine can affect the absorption of other oral medications. Such medications should be taken 1 hour before administration of cholestyramine on any day or per other guidance in the package insert. Watch for bleeding abnormalities due to vitamin K deficiency for which intravenous vitamin K may be administered.

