5.8 Duration of Study Participation

Participants may be removed from the study as a whole at any time at their own request, or they may be withdrawn at the discretion of the investigator for safety, behavioral or administrative reasons. The reason(s) for discontinuing study participation should be documented and may include:

- Completion of 12 months of active follow up after the end of protocol treatment
- Disease progression per mSWAT, after completing the End of Treatment assessments
- Disease progression per mSWAT during active follow-up
- Withdrawal of consent
- Participant is lost to follow-up. All attempts to contact the participant must be documented.
- At the discretion of the investigator for safety, behavioral, study termination or administrative reasons

Documentation of the reason for discontinuing study participation and the date effective should be made in the Electronic Health Record/medical record and appropriate eCRF

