- bb. Clinical testing must demonstrate teriflunomide plasma levels less than 0.02 mg/L or 0.02 µg/ml by two separate tests at least 14 days apart. If plasma levels are higher than 0.02 mg/L or 0.02 µg/mL, additional cholestyramine treatment will be considered.
- cc. Participants will receive leflunomide orally on a daily basis which will be recorded on the pill diary ([Appendix D](#)). The first 3 loading doses will be given at a dose of 100 mg, after which treatment will continue at a dose of 20 or 10 mg daily. See administration details in [Section 5.3](#).

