14.3 Expedited Reporting

The table below indicates what events to report to expeditiously (Table 14.3).

Table 14.3 Expedited Reporting Guidelines

Time point	What to report
From signing of the consent to study completion	
• All UPs and AEs that meet the definition of a UP
For the time period beginning at treatment through 90 days following cessation of treatment, or 30 days following cessation of treatment if the subject initiates new anticancer therapy, whichever is earlier	
• All SAEs regardless of relationship to protocol therapy• All AESIs, overdose• AESIs (Section 14.2)- irAEs, overdose

All reportable events will require follow up until stabilization or resolution per the agreement of the Study PI.	
From Day 1 of protocol therapy up to 90 days post-last leflunomide dose	
• Pregnancies and lactation
Post Safety follow-up to removal from study	
• All SAEs that are at least possibly related to leflunomide.
NOTE: All events reported expeditiously require follow-up reporting until the event is resolved, stabilized, or determined to be irreversible by the investigator.	

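### The three-month contraception floor and the 90-day pregnancy/lactation reporting row are not linked to the protocol's own teriflunomide elimination check

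*Combined protocol and SAP*

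**What the plan says.** **Contraception.** Inclusion criterion 18 applies to women and men of childbearing potential and runs "for the course of the study through at least three months after the last dose of protocol therapy". It warns of possible teratogenic or abortifacient effects. Section 17.6.1 adds that animal testing found embryolethality and teratogenicity.

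**Pregnancy reporting.** The pregnancy and lactation row of Table 14.3 runs "From Day 1 of protocol therapy up to 90 days post-last leflunomide dose". Other rows cover unanticipated problems to study completion and, after safety follow-up until removal from study, "All SAEs that are at least possibly related to leflunomide".

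**Elimination check.** Table 10.0 footnote bb states: "Clinical testing must demonstrate teriflunomide plasma levels less than 0.02 mg/L", on two separate tests 14 or more days apart. Section 5.5 describes the same check. If a level is too high, the only stated consequence is that "additional cholestyramine treatment will be considered".

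**Cholestyramine course.** The plan is 8 g three times daily for 11 days for everyone, but Section 5.5 is flexible: "It will not be a deviation if an administration of cholestyramine is delayed or if the 11 days are not consecutive", and "Cholestyramine administration may be adjusted per the discretion of the treating investigator".

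**Leaving the study.** One listed reason in Section 5.8 is "Disease progression per mSWAT, after completing the End of Treatment assessments". Withdrawal of consent and loss to follow-up are also listed, with no such condition. Section 17.5 allows withdrawal from all procedures and all further data collection. Participants without progression enter 12 months of active follow-up (Section 5.7).

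**The concern.** The protocol recognises that the metabolite persists, that levels vary widely between patients, and that elimination should be shown by assay. Its two pregnancy-related rules nevertheless end on fixed dates that ignore the assay. A participant of childbearing potential who leaves the study with an unfinished cholestyramine course, or with no passing results, satisfies criterion 18 by stopping contraception at three months. A pregnancy first reported after day 90 falls outside the one row written for it, even if clearance was never shown.

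What is at stake is possible fetal exposure in a very small number of people. Sample size, the response-rate estimate and its confidence interval are unaffected.

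**Working it through.** **1. The plan's own figure.** The three-month (90-day) period is stipulated. No derivation is given, so there is nothing to reproduce.

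**2. Text comparison.** Criterion 18 and the pregnancy row of Table 14.3 name no drug level. Section 5.5 and footnote bb name the level but say nothing about contraception or pregnancy reporting. There is no cross-reference in either direction.

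**3. Inputs.**
- Teriflunomide on 20 mg/day: mean 42 mg/L, range 3–150 mg/L, in one study (Section 2.2).
- Half-life about 2 weeks (Sections 2.2 and 8.1.4). Check: 56 days is 4 half-lives, and 1 − 2^(−4) = 93.8% of steady state. This agrees with the protocol's statement that nearly two months are needed without a loading dose.
- Cholestyramine in healthy volunteers: a fall of about 40% in 24 h, and 49–65% in 48 h (Section 2.5).
- Limit: 0.02 mg/L.

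**4. No cholestyramine.** C(90) = C0 × 2^(−90/14) = C0 × 0.0116. Day on which 0.02 is reached = 14 × log2(C0/0.02). The earliest second pass is 14 days later.

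| C0 (mg/L) | Level at day 90 | Multiple of 0.02 | Day 0.02 reached | Earliest second pass |
|---|---|---|---|---|
| 3 | 0.035 | 1.7 | 101 | 115 |
| 42 | 0.49 | 24 | 154 | 169 |
| 150 | 1.74 | 87 | 180 | 194 |

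Sensitivity to half-life: 90 days would be just enough without cholestyramine at half-lives of 12.5, 8.2 and 7.0 days from 3, 42 and 150 mg/L. At 21 days, the day-90 levels would be 0.15, 2.15 and 7.69 mg/L.

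**5. Full 11-day course, then natural decay.** Assume that cholestyramine starts at the last dose and that the volunteer rate holds for all 11 days. The fraction left at day 11 is 0.51^5.5 = 0.0246, 0.35^5.5 = 0.0031 or 0.60^11 = 0.0036. Multiply by 2^(−79/14) = 0.0200 to reach day 90.

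| Rate | From 3 | From 42 | From 150 |
|---|---|---|---|
| 49% per 48 h | 0.0015 | 0.021 | 0.074 |
| 65% per 48 h | 0.0002 | 0.0026 | 0.0093 |
| 40% per day | 0.0002 | 0.0030 | 0.011 |

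Only the slowest rate leaves a level above 0.02 at day 90: marginally from the mean, and by a factor of 3.7 from the maximum.

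**6. Shortened course.** With 5 days of cholestyramine and then 85 days of natural decay, the day-90 level is 0.045–0.116 mg/L from 42 and 0.16–0.41 from 150 over the three rates. In this model a delayed or split course gives the same day-90 level as a prompt one, provided all 11 days are completed by then. Delay matters because the participant may leave before finishing, and because the tests move later.

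**7. One repeat 11-day course from day 14, slowest rate.** From 42 mg/L: day 14 is 42 × 0.0246 × 2^(−3/14) = 0.89, and day 25 is 0.89 × 0.0246 = 0.022. The limit is reached at about day 27, with a second pass at about day 41. From 150 mg/L: 3.19, then 0.078, with the limit reached at about day 53 and a second pass at about day 67. At the two faster rates the level is below 0.02 by the end of the repeat course (day 25), so both passes are possible by about day 39.

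**8. Planned tests after a single course.** End of Treatment Day 14 passes only from starting levels below 0.9, 7.5 or 6.4 mg/L (49% and 65% per 48 h, 40% per day). Day 30 passes only below 2.1, 16.5 or 14.1 mg/L. From the mean of 42, both tests fail at every rate, so a first failure would be common under this model.

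**The case against.** The strongest reply is that the protocol already covers nearly everyone. Non-progressors remain on study, and so under contraception, for up to 12 months. Progressors leave after the End of Treatment assessments, footnote bb says that testing must show clearance, and footnote i lets the Day 30 visit move to match the final teriflunomide test. Read together, these make two passes the natural exit condition for progressors, although no sentence says so. Cholestyramine is prescribed for everyone and can be repeated. The three-month figure is a floor and permits longer. All of this stands, and it confines the gap to a minority of at most 14 patients.

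It is also true that retesting cannot reach someone who is lost or who withdraws from all data collection. For them only advice given in advance or at exit can work, and such advice may already be in the consent pages, which were not available.

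What the reply does not remove is the missing link. A participant can leave uncleared without breaching criterion 18 once three months have passed, and the pregnancy row closes at day 90 for everyone, including those still in active follow-up.

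Three stronger readings are tempting and are not supported:
- A reader might infer that 90 days is too short for the typical participant. A full course usually clears by then at the stated rates, and one repeat course does so at every constant rate.
- A reader might infer that a level above 0.02 mg/L is shown to be harmful to a fetus. The documents use that figure only to verify elimination.
- A reader might infer that late pregnancies go wholly unreported. Unanticipated problems and possibly related serious events remain reportable under other rows of Table 14.3, although neither row names pregnancy.

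**Conclusion.** The point holds as a modest safety-text gap and a cheap improvement. It concerns two groups. The first is participants of childbearing potential who exit without two documented passing results, through withdrawal, loss to follow-up, or a skipped, shortened or delayed cholestyramine course. The second is anyone not cleared by day 90, for the reporting row only.

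If no cholestyramine is taken, the day-90 level exceeds the protocol's limit by about 1.7 to 87 times over the stated concentration range. After a full course the excess is nil or small, except from high starting levels at the slowest rate.

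These figures rest on one-compartment decay with a 14-day half-life, a concentration range from another patient population, and volunteer data extrapolated beyond 48 hours. The protocol's figure of up to two years refers to non-detectable levels, a different limit, and is not used here. The number of participants affected cannot be estimated from the documents.

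**What to change.** In criterion 18 and in the pregnancy/lactation row of Table 14.3, state that contraception and reporting run until the later of (a) 90 days after the last leflunomide dose and (b) the two passing teriflunomide results already required by Section 5.5 and footnote bb. If the planned tests do not give two passes, retest before contraception is released. Leave repeat cholestyramine to the investigator, as now. Give anyone who withdraws before clearance is shown written advice to continue contraception until cleared or to an investigator-set maximum. That advice is the only part that can help those who cannot be retested.

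The costs are an amendment with matching consent wording, and about two extra blood levels for each participant not cleared at the planned tests (more if a retest falls before the limit is reached). Contraception beyond day 90 would be 0–15 days from 42 mg/L and 0–40 days from 150 mg/L after one full course. With no cholestyramine it would be about 25, 79 and 104 days from 3, 42 and 150 mg/L. These are minimums, because they assume a test on the day the limit is reached. The extension also binds unsterilised men, whom criterion 18 counts as being of childbearing potential. The sponsor should decide whether that is intended.
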